4.6 Strategies for Recruitment and Retention

Subjects will be recruited primarily from the HFpEF Program at Weill Cornell Medicine. Cardiology, Geriatrics, and Primary Care clinics may be screened in addition if necessary. Approximately 70% of patients seen between July 2018-October 2019 in the HFpEF clinic would be eligible to participate. By 2020 the HFpEF Program will see >200 unique patients, which will provide a sufficient number of subjects to enroll from. We plan to enroll 16 subjects.

The research assistant will screen subjects scheduled in the HFpEF Program in advance of their appointments to identify potentially eligible subjects. The research assistant will then introduce the study to each eligible subject and conduct the informed consent process. A screening and enrollment log will be kept by the research assistant. Subjects will receive \$50 upon consenting, randomization, and completing the baseline assessment. All subjects will provide written informed consent and HIPAA notifications.

We will not enroll the following vulnerable populations:

- Pregnant women
- Children
- Those who lack capacity to consent
- Employee/student volunteers

Planned enrollment is estimated based on frequencies observed in the HFpEF Program at Weill Cornell Medicine. Frequencies in the HFpEF Program are as follows:

- 57% Women
- 62% White non-Hispanic
- 16% Black non-Hispanic
- 11% Hispanic/Latino

Strategies for Retention: There are several opportunities to engage subjects to ensure retention. We will contact subjects weekly to instruct them to complete standardized web-based patient-reported outcomes questionnaires. Subjects will be asked to complete these assessments on their tablet computer (which we will provide free-of-charge and has internet capabilities), over the phone, or via email. We will also conduct routine phone calls for safety purposes (at this time, we can remind subjects to complete the weekly assessments if needed). For subjects who do not complete the assessments (we will track this electronically), we will call them daily to remind them and/or assist them with completing the assessments over the phone. If we are unable to contact the

subject over the phone, when applicable, we will attempt contact via email. To ensure pragmatism and enhance retention, assessments will be short and subject to change per subject feedback. Based off of subject feedback, we may eliminate subject phone calls on the last two weeks of each period. To maximize compliance and retention, subjects will receive \$50 at the end of successful completion of each phase up to 4 total phases (baseline and the 4 treatment periods). They will receive an additional \$50 as a compliance bonus at the end of period 4/end of study. In total, **subjects** will receive up to \$300. We will define compliance as attending 100% of scheduled visits and completing 90% of assessments during the defined time period.

Subjects may receive reimbursement for unanticipated fees, per PI discretion.

5. Registration Procedures

5.1 Subject Registration (WCM only)

Subjects will be registered within the WRG-CT as per the standard operating procedure for Subject Registration.

6. Study Procedures

6.1 Schedule of Assessments

| | Baseline | Research Intervention Phase | | | | | Post Intervention Phase | | |
|--|----------|-----------------------------|--------|----------|--------------------|--------------------------------------|-------------------------|-------------------|--------------------|
| | | Daily | Weekly | Biweekly | End of Periods 1-3 | End of Intervention Phase (Period 4) | 6 Month Follow-up | 9 Month Follow-up | 12 Month Follow-up |
| Informed Consent | | | | | | | | | |
| Randomization | | | | | | | | | |
| Demographics | | | | | | | | | |
| Medication Inventory | | | | | | | | | |
| Baseline Beta-Blocker Use | | | | | | | | | |
| Physical Exam | | | | | | | | | |
| Central Blood Pressure | | | | | | | | | |
| Electrocardiogram | | | | | | | | | |
| Cardiopulmonary Exercise Test ² | | | | | | | | | |
| Blood Draw for Troponin & NT-proBNP ³ | | | | | | | | | |
| Blood Draw for Future Research ⁴ | | | | | | | | | |
| Six-Minute Walk Test | | | | | | | | | |
| Short Physical Performance Battery | | | | | | | | | |
| Qualitative Interview | | | | | | | | | |
| Typology Question | | | | | | | | | |
| Health Literacy | | | | | | | | | |
| Number Literacy | | | | | | | | | |
| Short Graph Literacy | | | | | | | | | |
| Data Preferences | | | | | | | | | |
| EQ5d-VAS | | | | | | | | | |
| PROMIS-29 | | | | | | | | | |
| PROMIS-SF 6A | | | | | | | | | |
| PROMIS-Sexual Function | | | | | | | | | |
| KCCQ-12 | | | | | | | | | |

² Cardiopulmonary Test to occur only at the end of Period 1 and Period 2. Cardiopulmonary test to be accompanied by a blood draw for NT-proBNP and Troponin.

³ Blood samples will be collected for Troponin and NT-proBNP at the end of each period. In addition, on visits where the subject performs a Cardiopulmonary Test, we may collect blood for Troponin and NT-proBNP directly after the cardiopulmonary test.

⁴ Optional component of this study. Blood will be drawn at baseline, as well as at the end of Period 1 and Period 2

| | | | | | | | | | | |
|--|---|---|---|--|--|---|---|---|---|---|
| Decision Making Outcomes Questionnaires ⁵ |  | | | | |  | | | | |
| Dose Modification | | |  | | |  |  | | | |
| Telephone Call ⁶ | | |  | | | | | | | |
| Step Count Collection | |  | | | | | | | | |
| Remote Monitoring | |  | | | | | | | | |
| Interim Events History | | |  | | |  |  |  |  |  |
| Assessment of Beta-Blocker Usage | | | | | | |  |  |  | |

| Legend | |
|---|--------------------------------------|
|  | In-Office visit |
|  | Conducted Remotely |
|  | Conducted via Telephone |
|  | Collected via Garmin wearable device |

⁵ Decision Making Parameters Questionnaire to consist of Decision Conflict Scale, Decision Conflict Subscales, Patient Activation Measures Survey, Shared Decision-Making Questionnaire (SDM-1-9) and Revised Patient Attitudes Towards Deprescribing (rPATD)

⁶ Telephone contact to occur the day prior to, the day of, and the day following a dose modification. Telephone calls may be eliminated per subject feedback during the last two weeks of each period.

6.1.1 Baseline In-Person Visit

- Informed consent
- Randomization
 - Eligible subjects will be randomly assigned to into Arm 1 (ABAB) or Arm 2 (BABA) with a 1:1 ratio using a computer-generated randomization scheme developed by the data manager. Arm 1 will be on an On-Off-On-Off (ABAB) drug scheme, while Arm 2 will be Off-On-Off-On (BABA)
- Demographics
- Medication Inventory
- Baseline beta-blocker use
- Physical Exam, including vital signs
- Central blood pressure assessment via the UScom BP+ device
 - This device measures central and brachial blood pressure and blood pressure waveforms at the heart, as well as in the arm.
- Electrocardiogram
- Blood draw for Troponin & NT-proBNP
- Blood draw for future research
- Six-Minute Walk Test
- Exercise test used to assess aerobic capacity endurance. The distance covered over 6 minutes is used as the outcome by which to compare changes in performance capacity.
- Short Physical Performance Battery
 - Combines the results of gait speed, chair stand and balance tests as a predictive tool for possible disability and can aid in the monitoring of function in older people
 - Gait Speed: assesses the subject's lower extremity function
 - Chair Rise: assesses core strength
 - Balance Test: assess the subject's ability to stand unassisted without the use of a cane or walker
- Qualitative interview on understandability of study purpose and design
- Typology Questionnaire
- Health Literacy Questions
- Number Literacy Questions
- Short Graph Literacy
- EQ5D Visual Analogue Scale
- PROMIS-29
- PROMIS-SF 6A
- PROMIS-Sexual Function
- KCCQ-12
- Decision Making Outcomes Questionnaires
 - Decision Conflict Scale
 - Decision Conflict Subscale
 - Patient Activation Measure (PAM) Survey
 - Shared Decision Making Questionnaire
 - Revised Patient Attitude Towards Deprescribing Questionnaire (rPATD)

6.1.2 Treatment Phase

6.1.2a Daily

- Remote Monitoring
 - Remote monitoring will collect vital sign data, including blood pressure and heart rate via a free of charge remote monitoring platform already in use in the HFpEF Program. Data will be reviewed weekly. If we encounter “Red Flags”, we will call the subject to assess symptoms, and determine the need for medical attention and/or study withdrawal in consultation with the subject’s other physicians and the DSMB.
 - Red Flags are as follows:
 - Blood pressure >160/90 mmHg or <100/60 mmHg
 - Heart Rate >100 bpm or <50 bpm
- Step Count
 - Daily step count will be collected via Garmin wearable devices that will be provided to subjects during the duration of the treatment phase of the trial.

6.1.2b Weekly

- Dose modification (as described in section 3.1)
- Telephone Contact on the day prior to the dose modification, the day of the dose modification and on the day following dose modification. Telephone calls may be eliminated during the last 2 weeks of each period per subject feedback.
- Patient Reported Outcomes (PROMIS-29, PROMIS-SF 6A) via web-based surveys taken at home on tablet computers provided to each subject, over the phone, or via email – frequency/length of surveys may be decreased per subject feedback
- Interim Events History (Adverse Events/SAE) will be asked during each phone call

6.1.2.c Biweekly

- Kansas City Cardiomyopathy Questionnaire (KCCQ-12)

6.1.2d End of Periods

- Medication Inventory
- Dose Modification
- Physical Exam, including vital signs
- Central blood pressure assessment via the UScom BP+ device, when possible
- Electrocardiogram
- Six Minute Walk Test
- Cardiopulmonary Exercise Test (at the end of Period 1 and Period 2)
 - We may draw additional blood for Troponin & NT-proBNP directly after the CPET. On visits which include a CPET, the subject may have Troponin and NT-proBNP drawn twice.
- Blood Draw for Troponin & NT-proBNP
- Blood draw for future research (at end of period 1 & end of period 2 only)
- Short Physical Performance Battery
- Qualitative interview on understandability and usability of study materials
- EQ-5D VAS
- PROMIS-29
- PROMIS-SF 6A
- PROMIS-Sexual Function

- Kansas City Cardiomyopathy Questionnaire (KCCQ-12)
- Interim Events History

6.1.2e End of Intervention Visit Period

- Medication Inventory
- Dose Modification
- Physical Exam
- Central blood pressure assessment via the UScom BP+ device
- Electrocardiogram
- Six Minute Walk Test
- Short Physical Performance Battery
- Qualitative interview on understandability and usability of study materials
- Typology Question
- EQ5D-VAS
- PROMIS-29
- PROMIS-SF 6A
- PROMIS-Sexual Function
- Kansas City Cardiomyopathy Questionnaire (KCCQ-12)
- Interim Events History

6.1.2f Unscheduled Visits

Unscheduled visits may be performed at any time during the study. The unscheduled visits may occur on-site or as a telephone visit. All data recorded during unscheduled visits will be recorded in REDCap. Depending on the reason for the unscheduled visit, appropriate assessments will be performed based on the judgement of the investigator and the results will be recorded in the REDCap.

6.1.3 Follow-up Phase

Six, nine, and twelve months after the end of intervention, the study team will access the subject's electronic health record to assess the following:

- Interim Events History
- Determine whether subjects are taking beta-blockers or not
- PROMIS-29
- PROMIS-SF 6A
- PROMIS-Sexual Function

The study team will conduct a phone call or Zoom meeting with the subject to review this information and confirm survey completion. Surveys will be sent out to the subjects the week of their six-, nine-, and twelve-month follow-ups via their tablet computer provided by the study team, through email, or over the phone. A qualitative interview will also take place at the 6, 9, and 12-month follow up periods. This qualitative interview will be audio recorded and transcribed by a professional transcribing service. We will store the audio recordings obtained from the interviews three years after data analysis completion. These recordings will then be erased permanently.

Positive indications from study participants about a hospitalization or possible events at other institutions will be followed by collection of selected medical records. Records will include administrative hospital codes and copies of relevant portions of the medical record, including

admission and discharge notes, progress notes, laboratory studies, ECGs, radiographic studies, and any other diagnostic testing or procedure notes. We will obtain an appropriate consent for release of information prior to obtaining medical records.

For patients who have expired prior to the time of first contact for consent, we will contact the next of kin to obtain authorization to request/receive information about the cause of death and hospitalizations/emergency room visits leading up to the patient's death. In this scenario, the next of kin will provide verbal consent and asked to provide a release of medical information form.

7. Study Intervention

7.1 Study Intervention/Device Description

Beta-blockers, also known as beta-adrenergic blocking agents, work by blocking the effects of epinephrine. Although the benefits of beta-blockers in HF with reduced ejection fraction are well documented, RCTs of beta-blockers in HFpEF have been neutral to date, failing to consistently improve or worsen long-term outcomes including mortality and hospitalization rate. Beta-blockers do not provide symptomatic improvement in all subjects; some may feel better while other may feel worse after initiating this drug class. This is supported by opposing pathophysiologic mechanisms highlighted in the literature—on the one hand, beta-blockers can slow down heart rate, improve left ventricular filling, and thus improve cardiac output and overall functioning. On the other hand, beta-blockers can exacerbate chronotropic incompetence, worsen cardiac output, and reduce exercise tolerance. Beta-blockers are also a common cause of adverse drug reactions and can worsen function in some older adults. There is no readily discernable way to determine which patients will feel better and which will feel worse.

All subjects will have been taking beta-blockers prescribed by their physician prior to enrollment. The study team will provide the subjects dosage instructions based on the down-titration/up-titration schedule outlined in this protocol.

The study team will not provide study drug to the subjects. Subjects will continue to obtain their beta-blockers in the same manner as prior to study enrollment.

Beta-blockers may be contraindicated in the following subjects:

Relative contraindications:

- Asthma; COPD (use cardio-selective β blockers/ β -1 selective)
- Psoriasis
- Symptomatic bradycardia
- Sick sinus syndrome (without a pacemaker); heart block greater than first degree
- Peripheral artery occlusive disease, Raynaud phenomenon
- Pregnancy
- Atenolol is absolutely contraindicated in pregnancy

Absolute contraindications:

- Allergy
- Cardiogenic shock and hypotension
- Pheochromocytoma

These contraindications are less relevant because these issues would have already been considered by their usual prescribing physicians prior to the study. To be clear, we will not be initiating a new prescription of beta-blocker for subjects; all subjects enrolled will have already be prescribed beta-blocker at the time of enrollment into the study.

7.2 Availability

Subjects will have been prescribed beta-blockers by their physician. Subjects will thus continue to obtain their beta-blockers in this manner. When modifications are made to the dosage, the study team will advise if their tablet or pill may be halved. In instances where the pill cannot be halved, the study team will prescribe a new dosage, which will be sent to the subject's pharmacy.

7.3 Acquisition and Accountability

Prescriptions for beta-blocker may be provided by prescribers in the HFpEF Program as needed.

7.4 Dosing and Administration

We have created a down-titration schedule, where we will reduce the dose of each beta-blocker by 50% every week, a schedule used in a prior deprescribing study of antihypertensives, that included beta-blockers. This schedule accounts for a sufficient number of half-lives to ensure drug clearance and accounts for changes in receptor density and related adrenergic hypersensitivity linked to withdrawal symptoms and ADWES observed after abrupt beta-blocker cessation. Re-initiation/up-titration will be done in reverse order. Subjects will never go on a dosage higher than their usual home dose. All drugs will be administered orally. To assist subjects with dose reduction, each subject will receive pill cutters.

| Table 4: Examples of drug down-titration schedule for selected β-blockers | | | | | |
|--|---------------|---------------|---------------|---------------|-----------------|
| Examples | Week 1 | Week 2 | Week 3 | Week 4 | Week 5+6 |
| Metoprolol 200mg daily | 100mg daily | 50mg daily | 25mg daily | 12.5mg daily | Off |
| Carvedilol 50mg BID | 25mg BID | 12.5mg BID | 6.25mg BID | 3.25mg BID | Off |
| Bisoprolol 10mg daily | 5mg daily | 2.5mg daily | Off | Off | Off |
| Atenolol 100mg daily | 50mg daily | 25mg daily | 12.5mg daily | Off | Off |
| Betaxolol 20mg daily | 10mg daily | 5mg daily | 2.5mg daily | Off | Off |
| Nebivolol 40mg daily | 20mg daily | 10mg daily | 5mg daily | Off | Off |
| Nadolol 320mg daily | 160mg daily | 80mg daily | 40mg daily | Off | Off |
| Propranolol 40mg BID | 20mg BID | 10mg BID | 5mg BID | Off | Off |
| Acetbutolol 600mg BID | 300mg BID | 150mg BID | 75mg BID | Off | Off |
| Penbutolol 80mg daily | 40mg daily | 20mg daily | 10mg daily | Off | Off |
| Pindolol 30mg BID | 15mg BID | 7.5mg BID | Off | Off | Off |
| Labetalol 1200mg BID | 600mg BID | 300mg BID | 150mg BID | Off | Off |

7.4.1 Dosing Delays/Dose Modifications

We do not anticipate any dosing delays or dose modifications outside of the aforementioned down-titration and up-titration schedule. However, dosing changes and other adaptations to the dosing schedule will be up to the discretion of the PI if clinical findings arise.

7.5 General Medication Inventory and Supportive Care Guidelines

All concomitant medications will be recorded and/or updated on subject medication log throughout the course of the study.

7.6 Duration of Therapy and Criteria for Removal from Study

We do not anticipate treatment delays. In the setting of a treatment delay due to an adverse event, continued study participation will depend on:

- Disease progression
- Intervening illness that prevents further administration of treatment,
- Unacceptable adverse event(s),
- Subject decision to withdraw from the study,
- General or specific changes in the subject's condition render the subject ineligible for further treatment in the judgment of the investigator.

7.7 Duration of Follow Up

Six, nine, and twelve months after the end of intervention we will access the electronic health record to assess vital status, hospitalizations, emergency department visits and whether or not the subject is taking a beta-blocker.

7.8 Measures to Minimize Bias: Randomization and Blinding

This study will not be blinded. The study team will conduct randomization using a WCM-approved randomization tool.

7.9 Study Intervention/Follow-up Compliance

Study team will ensure the protocol is followed as written. Protocol can be modified per subject feedback.

Remote monitoring will occur on a daily basis. Subjects will be provided with a tablet computer and blood pressure cuff free-of-charge. These data will be automatically uploaded to an online portal, which we will review weekly.

Telephone calls will occur on a weekly basis, during each call we will request information regarding drug compliance. Telephone calls may be eliminated during the last 2 weeks of each period. If unable to contact the subject via telephone, we will attempt through email.

For subjects that are potentially lost to follow-up, we will make at least four attempts to contact them, in a 4-week time frame, via telephone and/or email. We will also inquire about their status from their physician, as well as through their electronic health records.

A subject will be considered lost to follow-up if we are unable to contact them after 4 attempts in 4 weeks.

7.10 Blood for Future Research

Subjects will be given the opportunity to participate in a voluntary component of the study, where we will draw blood samples for future research. Subjects will be informed of risks, benefits and alternatives. Up to 30 ml of blood will be obtained. For subjects who have a blood specimen that is insufficient in volume, a repeat blood draw may be performed at their next visit.

Blood draws for future research will follow similar processing and storage procedures as outlined in a companion WCM-approved IRB (Protocol 19-05020216 – Next Generation Sequencing & Molecular Characterization of Cardiovascular Diseases) that supports the HFpEF/Cardiovascular biobank.

Subjects who consent to this additional component will have an additional 2 tubes of blood drawn at the baseline visit, as well as at the end of period 1 and end of period 2.

8. Study Intervention Discontinuation and Subject Discontinuation/Withdrawal

8.1 Discontinuation of Study Intervention

If consented subjects are intolerant or unwilling to proceed with dose modification, we will continue to follow them through the course of the study (if subject is willing). Remaining study procedures will be completed as indicated by the study protocol. If a clinically significant finding is identified (including, but not limited to changes from baseline) after enrollment, the investigator will determine if any change in subject management is needed. Any new clinically relevant finding will be reported as an adverse event (AE).

The data to be collected at the time of study intervention discontinuation will include the following:

- Concomitant Medications
- Decision making outcomes questionnaire
- Short Physical Performance Battery
- Adverse Events/SAE

8.2 Subject Discontinuation/Withdrawal from the Study

Subjects are free to withdraw from participation in the study at any time if they wish.

An investigator may discontinue or withdraw a subject from the study for the following reasons:

- Pregnancy
- Significant study intervention non-compliance
- If any clinical adverse event (AE), or other medical condition or situation occurs such that continued participation in the study would not be in the best interest of the subject (this will be decided on conjunction with their own physician and/or the DSMB).
- Disease progression which requires discontinuation of the study intervention
- If the subject meets an exclusion criterion (either newly developed or not previously recognized) that precludes further study participation
- Subject lost to follow-up after several attempts to contact subject to schedule study visit.

The reason for subject discontinuation or withdrawal from the study will be recorded on the Case Report Form (CRF) in REDCap. Subjects who sign the informed consent form and are randomized but do not receive the study intervention may be replaced. Subjects who sign the informed consent form, and are randomized and receive the study intervention, and subsequently withdraw, or are withdrawn or discontinued from the study, will be replaced.

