| Study Description: | We will determine whether N-of-1 trials, as a pragmatic, patient-centered approach to medication optimization that can overcome key barriers of deprescribing, can lead to increased subject confidence regarding the decision to continue or discontinue beta-blockers in older adults with Heart Failure with Preserved Ejection Fraction (HFpEF). |
| Sample Size: | N=16 |
| Enrollment: | This study will enroll 16 subjects. |
| Study Population: | Subjects will be recruited from the HFpEF Program, as well as from the Cardiology, Heart Failure, Geriatrics and/or Internal Medicine clinics at Weill Cornell Medicine. |
| Enrollment Period: | 30 Months |
| Study Design: | This is an unblinded NIH Stage 1 of Behavioral Intervention Development trial, using a Crossover intervention model. We will enroll 16 subjects and we will conduct four rounds of N-of-1 trials with four subjects each. We will use a two-arm crossover titration/reversal design (On [A] vs. Off [B]) with up to 4 periods. Subjects will be randomized to either ABAB or BABA (see Figure 1 below). Each period will last up to 6 weeks, allowing for sufficient time for up-titration and onset of drug action, and down-titration and washout. Each subject will have the option to participate in less (2-3) or more periods (5-6) depending on whether they need additional information to make an informed decision about continuing or discontinuing their beta-blocker at the end of this trial. The intervention drug will be beta-blockers, previously prescribed to the subjects by their physician. We have developed a titration algorithm, where we will reduce the dose of each beta-blocker by 50% every week. |
| Description of Sites/ Facilities Enrolling | |
| Subjects: | Enrollment will only be at Weill Cornell Medicine. |
| Study Duration: | Estimated Primary Completion Date of December 2022 |
| Subject Duration: | 1 Year |
| Study Agent/Device Name | Not applicable |

Intervention Description:

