The intervention is a two-arm crossover withdrawal/reversal design (On [A] vs. Off [B]) with up to 4 periods, each period lasting up to 6 weeks. During the On period (A), subjects will be on their beta-blocker. During the Off period (B), their beta-blockers will be down-titrated and subsequently discontinued; we will decrease the dose of beta-blocker by 50% every week regardless of which beta-blocker they are on, similar to an algorithm used in a prior deprescribing trial. Subjects will be randomized to either ABAB or BABA (see Figure 1 below).

Subjects may be on any of the following beta-blockers:

- Atenolol
- Betaxolol
- Bisoprolol
- Metoprolol
- Metoprolol Succinate
- Metoprolol Tartrate
- Penbutolol
- Nebivolol
- Propranolol
- Acebutolol
- Pindolol
- Carvedilol
- Labetalol
- Nadolol
- Sotalol
- Nadolol

Co-Primary Objectives:

To determine the features of a feasible and pragmatic protocol for deprescribing N-of-1 trials in patients with Heart Failure with Preserved Ejection Fraction.

Funded by National Institute on Aging

To compare physical activity between the On and Off phase via:

- Step Count collected via Garmin wearable device

Funded by the New York Community Trust

To compare exercise capacity between the On and Off phase via:

- Peak oxygen consumption (VO₂) Cardiopulmonary Exercise Test

Funded by the New York Community Trust

To compare lower extremity function between the On and Off phase via:

- Short physical performance battery (lower extremity function)

Funded by the New York Community Trust

Secondary Objective:

To compare Patient Reported Outcomes between the On and Off phase via:

- Kansas City Cardiomyopathy Questionnaire
- PRO Measurement Information System including PROMIS-29, PROMIS-Sexual Function, PROMIS-SF 6a and EQ5D Visual Analogue Scale (VAS)

Funded by the New York Community Trust

Exploratory Objectives:

We will explore whether N-of-1 trials can improve decision-making parameters, including decision conflict (measured by the Decision Conflict Scale), patient activation (measured by the Patient Activation Measure), Shared Decision Making (measured by the 9-item Shared Decision-Making Questionnaire), and attitudes toward deprescribing (measured by the revised patient attitudes toward deprescribing questionnaire).

Funded by National Institute on Aging

Primary Endpoints:

The features of a feasible and pragmatic protocol for deprescribing N-of-1 trials as measured by qualitative interviews.

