| Cerebrovascular accident | Emergent care if indicated including admission and necessary medications/interventions. Subject withdrawal from the study. |
| Myocardial infarction | Emergent care if indicated including admission and necessary medications/interventions. Subject withdrawal from the study. |
| Angina | Emergent care if indicated including admission and necessary medications/interventions. Subject withdrawal from the study. |
| Heart failure exacerbation | Emergent care if indicated including admission and IV diuretics. For non-emergent issues, standard review and adjustment of medications. Medical management including beta-blocker management as recommended by treating physician. If exacerbation unrelated to the study and not contraindicated following discussion between investigators and treating physician, subject will continue to follow protocol. |
| Shortness of breath | Evaluation of volume status, adjustment of medications. Medical management including beta-blocker management as recommended by treating physician. If exacerbation unrelated to the study and not contraindicated following discussion between investigators and treating physician, subject will continue to follow protocol. |
| Worsened hypertension | Emergent care if indicated including admission and IV antihypertensive agents. For non-emergent issues, standard review and management of oral medications. If unrelated to the study and not contraindicated following discussion between investigators and treating physician, subject will continue to follow protocol. |

14. Unanticipated Problems Involving Risks to Subjects or Others

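### Feasibility is measured only by interviews, yet no interview is scheduled when a subject leaves mid-period, so reasons for failure may be under-represented

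*Combined protocol and SAP*

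**What the plan says.** The synopsis gives the first primary endpoint as "The features of a feasible and pragmatic protocol for deprescribing N-of-1 trials as measured by qualitative interviews". No other measure of feasibility is named.

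Section 3.1 schedules interviews at consent, at completion of each period, at completion of the intervention phase, and at 6, 9 and 12 months afterwards. Sections 6.1.1, 6.1.2d, 6.1.2e and 6.1.3 agree. Section 3.1 also allows additional interviews, but these are optional and not tied to withdrawal.

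Two sections deal with subjects who do not carry on:

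- **Section 8.1** covers subjects who are intolerant of dose modification or unwilling to proceed with it. If willing, they stay in follow-up, and "Remaining study procedures will be completed as indicated by the study protocol". The sentence beginning "The data to be collected at the time of study intervention discontinuation will include the following" leads to four items: concomitant medications, the decision-making questionnaire, the Short Physical Performance Battery (SPPB) and adverse events.
- **Section 8.2** covers leaving the study. The reason is recorded on the case report form. Subjects who are "randomized but do not receive the study intervention may be replaced"; those who received the intervention and "subsequently withdraw, or are withdrawn or discontinued from the study, will be replaced". Replacement is thus optional in the first case and mandatory in the second.

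The table of example actions in Section 13.4 includes, for worse or new arrhythmia, cerebrovascular accident, myocardial infarction and angina: "Emergent care if indicated including admission and necessary medications/interventions. Subject withdrawal from the study". The plan therefore foresees some exits that follow adverse events.

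Section 12.4.1, item 6, analyses the transcripts by directed content analysis and defines no analysis set.

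**The concern.** In a study of feasibility, the people who could not go on are among the most informative. The synopsis states "We will enroll 16 subjects and we will conduct four rounds of N-of-1 trials with four subjects each". Section 12 describes the process as iterative, and Section 7.9 lets subject feedback modify the protocol. A failed attempt in one round is direct input to the next.

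Because on-intervention interviews depend on completing a period, the schedule collects accounts of periods that worked and skips accounts of periods that did not. An Arm 2 subject who leaves during the first taper has been interviewed only at baseline, on whether the study purpose and design were understandable, before any study dose change. The reason field on the case report form is the only other item that Section 8.2 specifies. The feasibility findings could then rest too heavily on people who managed the protocol.

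**Working it through.** The plan states no figure on this point, so there is none to reproduce. The check is a reading of who is interviewed, followed by an illustration of size.

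**Who gives an interview about a failed period**

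| Subject | Scheduled interviews | Interview about the failed period? |
|---|---|---|
| Stops dose modification, stays in the study (8.1) | All remaining ones, if willing | Yes, at the next scheduled point |
| Leaves the study during Period 1 (8.2) | Consent only | No |
| Leaves the study during Period 2 (8.2) | Consent and end of Period 1 | No |

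The last two rows assume that a subject who has left the study gives no follow-up interviews; Section 8.2 provides for none.

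**Inputs**

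- Completers: 16 (synopsis), assuming that replacement restores this number and that replacements complete.
- Withdrawals after starting: w = 2, 3 or 4. This is assumed, because the documents give no rate.
- Interviews per completer: 1 (consent) + number of periods + 3 (follow-up), counting the end-of-intervention interview as the last period-end one. That is 1 + 4 + 3 = 8 for four periods and 1 + 2 + 3 = 6 for two, the minimum in Section 3.1.
- Each withdrawer leaves in Period 1, so gives 1 interview.

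**Formulas**

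- Share of treated subjects with no exit interview: w / (16 + w).
- Withdrawers' share of all interviews: w / (w + 16 × 8) for four-period completers, w / (w + 16 × 6) for two-period completers.
- Withdrawers' share of period-end interviews: 0 of 64 (16 × 4) or 0 of 32 (16 × 2).
- The same share with one exit interview each: w / (w + 64) or w / (w + 32).

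| w | Treated, no exit interview | Share of all interviews (4 / 2 periods) | Share of period-end interviews | With exit interview added (4 / 2 periods) |
|---|---|---|---|---|
| 2 | 2/18 = 11.1% | 2/130 = 1.5% / 2/98 = 2.0% | 0% | 2/66 = 3.0% / 2/34 = 5.9% |
| 3 | 3/19 = 15.8% | 3/131 = 2.3% / 3/99 = 3.0% | 0% | 3/67 = 4.5% / 3/35 = 8.6% |
| 4 | 4/20 = 20.0% | 4/132 = 3.0% / 4/100 = 4.0% | 0% | 4/68 = 5.9% / 4/36 = 11.1% |

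If the 4 withdrawers leave in Period 2 instead, each has given 2 interviews. Their share is then 8/136 = 5.9% or 8/104 = 7.7% of all interviews, and 4/68 = 5.9% or 4/36 = 11.1% of period-end interviews. None of these concerns the period that they left.

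**Does replacement cause this?** Take 20% withdrawal with no replacement: of 16 treated, 3.2 withdraw and 12.8 complete four periods. The withdrawers' share of all interviews is 3.2 / (3.2 + 12.8 × 8) = 3.2/105.6 = 3.0%, the same as with replacement (4/132). The gap comes from the missing exit interview and the shorter exposure.

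**PROs.** Section 6.1.2 collects PROMIS-29 and PROMIS-SF 6A weekly and KCCQ-12 biweekly, so values before exit exist. During the intervention, EQ-5D VAS and PROMIS-Sexual Function are listed only at period ends and at the end of intervention, so a mid-period exit leaves neither for that period.

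**The case against.** Much can be said for the plan. Section 8.1 keeps subjects who cannot or will not change dose, and keeps their interviews if they are willing. These are people for whom the protocol was hard to follow. Stopping after two periods counts as completion, which limits true withdrawals. Earlier transcripts from withdrawers exist, the reason for leaving is recorded, and extra interviews are permitted. The Section 13.4 table gives examples only, and for several events it provides for continuing on protocol under stated conditions. This is also a Stage 1 pilot not meant to establish efficacy.

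All of this stands and limits the point to subjects who leave the study under Section 8.2, and to those under Section 8.1 who are unwilling to continue. It does not supply an interview about the period in which they left.

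Two stronger readings are tempting. First, a reader might infer that withdrawers are swapped out and contribute nothing to the feasibility endpoint. The documents do not support this: the consent interview and any period-end interviews remain, and no text removes them. Replacement would select subjects only if those replaced were dropped from the analysis, on which the plan is silent.

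Second, a reader might infer that the On-Off contrasts are shifted by a calculable amount. The documents give neither a withdrawal rate nor any indication of who would leave. SPPB is on the Section 8.1 list, and step counts and several PROs are collected before exit. An early leaver may still lack data in the last-two-week window, but no shift in standard deviation units can be claimed.

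**Conclusion.** The point holds in a limited form. The plan has no scheduled interview for a subject who leaves the study mid-period, although interviews are the only measure of the first co-primary endpoint. Reasons for infeasibility may therefore be under-represented. With 2 to 4 withdrawals and full replacement, 11% to 20% of treated subjects would have no exit interview. If they leave in Period 1, they supply none of the period-end interviews. These sizes rest on assumed withdrawal numbers and on exits falling mid-period; whether anyone will leave that way is unknown. Mandatory replacement is not itself the fault. This is an inexpensive improvement worth making.

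**What to change.** 1. Add the existing end-of-period qualitative interview and the PROs to the list in Section 8.1, and add the same provision to Section 8.2, offered at exit to every subject who stops the intervention or leaves the study. The interview's stated topic is the understandability and usability of study materials, so a prompt on why the subject stopped would be useful.
2. As accompanying wording in Sections 8.2 and 12.4.1, state that data and transcripts from withdrawn and replaced subjects stay in the analysis and that replacements are added to them.
3. Report withdrawals and replacements by On/Off phase and reason as a feasibility result.

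The cost is protocol and analysis-plan wording, plus one extra use of an existing interview and questionnaire set per withdrawer who agrees. Some will decline, so the gap will narrow but may not close; the number declining should be reported. Clinical management does not change.
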